A feasibility study undertaken by the chief investigator (CI), as part of a PhD programme of study, determined that an ankle placement of the Actigraph GT3X accelerometer was superior to the waist for determination of body position and step count. In this study, thirty healthy adult volunteers simulated patients weakened by critical illness. They performed a movement protocol which incorporated the typical activities undertaken by patients recovering in hospital from critical illness. These included moving from lying to sitting, sitting to standing (and vice versa) and walking short distances. Video recordings were taken of each participant during the movement protocols, enabling observation of the body positions adopted and step counting during the walking activities. Video recording was used as the criterion measure for comparison against the data captured by the accelerometers worn both at the ankle and the waist. The activities detailed above are typically included within early mobility protocols which have undergone evaluation within populations experiencing critical illness (McWilliams et al., 2015, Adler and Malone, 2012, Schweickert et al., 2009). Moderate agreement ($\kappa = 0.43$, $p < 0.001$), was found between observation of video recordings of body position (lying, sitting or standing) and the inclinometer setting for the ankle placement. Fair agreement only ($\kappa = 0.21$, $p < 0.001$) was found for the waist placement. Regular misclassification of all body positions was found with the waist placement. The ankle placement identified both the lying and standing positions well. The sitting position however was only correctly identified intermittently for the ankle placement. A novel finding emerged from this research relating to the ankle placement site. When a side lying position was adopted, the ankle accelerometer inclinometer function regularly registered a '0'. The '0' setting normally corresponds to a 'not being worn' option. When a reading of '0' was recoded to the option 'side lying,' agreement improved from $\kappa = 0.43$ ($p < 0.001$) to $\kappa = 0.48$ ($p < 0.001$). This finding suggests a new way of interpreting the '0' reading of the inclinometer when worn on the ankle, which is worthy of further investigation within an actual patient population.

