3. To investigate the criterion validity of the combination of thigh and ankle accelerometer inclinometer outputs to correctly determine the sitting position. This

will determine whether an algorithm can be constructed using the two inclinometer readings, which will better distinguish the sitting from the standing position.

4. To evaluate, from a user perspective, the acceptability of these devices in relation to the placement sites used. This will be achieved by asking patients to score the answer to a particular question through the use of a Likert scale. The question is:
 - How would you rate the comfort of wearing the accelerometers?

In consideration of the results from the feasibility study undertaken by the CI and research using the addition of a thigh mounted accelerometer to identify the sitting position (Skotte et al., 2014), the following hypotheses can be constructed:

Hypotheses

1. An ankle mounted Actigraph GT3X accelerometer, will accurately identify both the lying and standing positions when compared with direct observation as a criterion measure.
2. An ankle mounted Actigraph GT3X accelerometer, will capture a step count comparable to that recorded by direct observation in a population resident on a hospital ward recovering from critical illness.
3. The combination of inclinometer outputs of both the thigh and ankle placement sites will permit development of an algorithm permitting the ability to better distinguish between the sitting and standing position.
4. The ankle and mid-thigh accelerometer placement sites will be well tolerated by patients recovering on a ward from critical illness.

Subject selection and involvement

The study will invite adult hospital ward patients recovering from critical illness to wear one Actigraph GT3X accelerometer on the antero-medial mid-thigh and another on the ankle, resting above the lateral malleolus of the same leg. The accelerometers will be worn for a period of time not exceeding three hours. Each device will be attached with a single patient use broad elastic belt, secured by Velcro fastening, using a standardised placement protocol. The non – dominant leg will be the preferred placement side.

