A sample size of 20 participants will be recruited. This sample size has been used in previous research investigating the validity of a different accelerometer model to quantify gait parameters in patients recovering from critical illness (Edbrooke et al., 2012). They predicted that 12 subjects were necessary based upon alpha = 0.05 (significance level), beta = 0.9 (power) and a correlation of $r = 0.75$, categorised as a good to excellent correlation (Trapp and Dawson, 2004). A sample size of 20 was also recruited in another study investigating the validity of accelerometer measurement within a hospitalised stroke population (Kramer et al., 2013). Recruiting a sample of 20 patients will permit some attrition should there be any accelerometer malfunction or decisions to withdraw, yet supply an achievable number for participant recruitment based on feedback from clinical colleagues working within the specialty.

Statistical analysis

IBM SPSS statistics (Version 20) will be used to undertake statistical analysis. Some data captured by the accelerometers is continuous and others categorical.

Categorical data

Categorical data, concerning body position (lying, sitting or standing) will be analysed using the Kappa statistic, calculating agreement between the accelerometer inclinometer data and direct observation. Each accelerometer placement site (thigh and ankle) will initially be analysed separately. Examination of the inclinometer raw data captured from both placement sites will determine whether an algorithm can be constructed using readings from both the ankle and thigh placement to improve determination of the sitting

position specifically if necessary. Direct observation will serve as the criterion measure for all the analyses.

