Percentage agreement of inclinometer raw data from the thigh and ankle accelerometers with direct observation for detection of each separate body position will be calculated. A further percentage agreement analysis will be undertaken if an algorithm can be constructed for determination of the sitting position using readings from both placement sites. This algorithm will be compared against direct observational raw data identifying the sitting position only. This result will be compared against the percentage agreement of the individual placement sites in determination of the sitting position. This will assist in determination of whether the algorithm is more superior to a single placement site in determination of the sitting position.

Continuous data

Agreement between step count recorded by each accelerometer placement site and direct observation (manual counts) as a criterion measure will be determined using Bland Altman analysis with 95% limits of agreement (LOA).

Acceptance of the devices over a three-hour period

The statements within the Likert scale will be collapsed to obtain true positives (very comfortable and somewhat comfortable) and true negatives (very uncomfortable and somewhat uncomfortable). The middle category (neither comfortable nor uncomfortable) will remain a separate category. A descriptive analysis will be undertaken to investigate this particular aspect of enquiry using percentages of true positives, the middle category and true negatives. This will be presented graphically.

Any specific comments made by the patients in relation to acceptability of the devices will be included as free text within the results section. The statements will be anonymous and permission from participants will be sought regarding their inclusion within the body of the thesis or publications which may arise from it.

Ethics approval

This study has received approval from the NHS Local Research Ethics Committee (REF: XXXXX) and the Research Ethics Sub Committee, YSJU (REF: XXXXXX).

Data handling and confidentiality

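### The one analysis named for the two-site algorithm, agreement on observed sitting, cannot by itself show that sitting is better distinguished from standing

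*Combined protocol and SAP*

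**What the plan says.** Objective 3 (Defining the research question) has two parts. The first is "To investigate the criterion validity of the combination of thigh and ankle accelerometer inclinometer outputs to correctly determine the sitting position". The second asks whether an algorithm can be built from the two readings "which will better distinguish the sitting from the standing position". Hypothesis 3 takes up only the second part: the combined outputs "will permit development of an algorithm permitting the ability to better distinguish between the sitting and standing position".

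The Categorical data section plans three things:

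- **Kappa** for body position, inclinometer against observation. On this it says "Each accelerometer placement site (thigh and ankle) will initially be analysed separately". It does not say whether kappa is later applied to the algorithm.
- **Percentage agreement** of the thigh and ankle raw data "for detection of each separate body position will be calculated". This is planned for the two devices, not for the algorithm's output.
- **A further percentage agreement** for the algorithm, if one can be built: "This algorithm will be compared against direct observational raw data identifying the sitting position only". Then: "This result will be compared against the percentage agreement of the individual placement sites in determination of the sitting position". The plan says this will help to decide whether the algorithm is superior to a single site.

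In the feasibility study (section on the Actigraph GT3X accelerometer), the ankle found sitting only intermittently, but "The ankle placement identified both the lying and standing positions well".

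**The concern.** Telling sitting from standing involves two errors: sitting called standing, and standing called sitting. The measure named for the algorithm appears to count only the first. A rule can raise its score simply by calling sitting more often, and the standing it then gets wrong would not appear in the planned comparison. The ankle already identified standing well in the feasibility study, so accuracy on standing is something a combined rule could lose.

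At stake is the claim that two sites are better than one. The algorithm is to come out of inspecting the study's own raw readings, so the yardstick should be fixed beforehand and should cover both error directions.

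**Working it through.** The plan states no figure on this point, so there is none to reproduce. The argument rests on the text. The numbers below use assumed inputs and only show what each measure can and cannot detect.

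**1. Natural reading: observed sitting epochs only.** The percentages for single sites are given per observed position, so the algorithm's figure is most naturally

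agreement = (observed sitting called sitting) / (all observed sitting).

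No standing or lying epoch enters the numerator or the denominator. Each sitting epoch called standing lowers the figure. A standing or lying epoch called sitting leaves it unchanged.

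**2. Two rules with the same planned score.** Assume 100 observed epochs of sitting and standing, and two rules that each get 90% of sitting right. Kappa = (po − pe)/(1 − pe), where po is observed and pe is chance agreement.

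| Sitting:standing | Standing correct | Planned figure | po | pe | Kappa |
|---|---|---|---|---|---|
| 80:20 | 90% | 90% | (72+18)/100 = 0.90 | 0.8×0.74 + 0.2×0.26 = 0.644 | 0.72 |
| 80:20 | 30% | 90% | (72+6)/100 = 0.78 | 0.8×0.86 + 0.2×0.14 = 0.716 | 0.23 |
| 50:50 | 90% | 90% | (45+45)/100 = 0.90 | 0.50 | 0.80 |
| 50:50 | 30% | 90% | (45+15)/100 = 0.60 | 0.50 | 0.20 |

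The planned figure does not separate them. At the limit, a rule that always answers sitting scores 100%, gets no standing right and has kappa 0.

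**3. Other reading: sitting versus not sitting over all epochs.** Assume 40 lying, 40 sitting and 20 standing epochs, 90% of sitting correct (36) and 10 false sitting calls. Agreement = (36 + 60 − 10)/100 = 86%. It is 86% if all 10 false calls fall on lying (0/20 = 0% of standing misread) and 86% if all 10 fall on standing (10/20 = 50% misread). False sitting calls now count, but standing errors are not isolated.

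**4. Why a pooled summary is not enough either.** Take shares of 50% sitting, 40% lying and 10% standing, and a rule that calls every upright epoch sitting and reads lying perfectly.

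- Sensitivity for sitting: 1.00.
- Pooled specificity: 0.40/0.50 = 0.80, so balanced accuracy = (1.00 + 0.80)/2 = 0.90.
- Sitting-versus-not kappa: po = 0.90, pe = 0.5×0.6 + 0.5×0.4 = 0.50, kappa = 0.40/0.50 = 0.80.
- Three-position kappa: pe = 0.5×0.6 + 0.4×0.4 + 0.1×0 = 0.46, kappa = 0.44/0.54 = 0.81.
- Specificity against standing: 0.00.

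Only the last line shows that the rule identifies no standing.

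**5. Pooled break-even, as illustration only.** Assume a best single site with sensitivity 0.75 and specificity 0.95, and an algorithm with sensitivity 0.85. The planned comparison shows +10 points whatever the specificity. Balanced accuracy ranks the algorithm lower once specificity falls by more than 10 points. Kappa does so after a fall of 5.33, 7.45, 10.00 or 13.11 points at sitting shares of 30%, 40%, 50% or 60%. These figures pool lying with standing, so they do not measure the sitting-versus-standing gap itself.

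**The case against.** The planned measure does bear on sitting versus standing. It falls with every sitting epoch called standing, and missed sitting is the weakness that the feasibility study reports for the ankle. A reader might infer that the plan ignores the contrast altogether. The documents do not support that: one of the two error directions is captured, and the first sentence of objective 3 is addressed.

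A reader might also infer that kappa is ruled out for the algorithm. It is not. The sites are to be analysed separately at first, and what follows is left open. But the only later step named is the sitting percentage.

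A third inference would be that the planned ranking will usually be wrong. That is not shown. Take one possible rule, sitting if either site reads sitting, with independent errors, thigh 0.75/0.95, ankle sensitivity 0.40 and an ankle false-sitting rate of 5% to 10%. Sensitivity is 1 − 0.25×0.60 = 0.85. Specificity is 0.95×0.95 = 0.9025 down to 0.95×0.90 = 0.855. Balanced accuracy is 0.876 to 0.853, against 0.850 for the thigh, so the planned ranking holds. On kappa it holds at 5% for all four sitting shares, and at 10% it reverses only at shares of 30% and 40%. These inputs are also assumed and pool lying with standing.

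Finally, the algorithm is conditional, the comparison is descriptive, and the objectives for single sites are untouched. All this limits the weight of the point. It does not supply the missing error direction.

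**Conclusion.** The point holds in a limited form. The one analysis named for the algorithm captures sitting called standing but, on the natural reading, not standing or lying called sitting. By itself it cannot establish hypothesis 3 or the second sentence of objective 3, and it could rank a rule that over-calls sitting as superior. The over-calling part depends on that reading. If sitting versus not sitting is meant, false sitting calls count, but standing errors are mixed with lying errors and the contrast is still not isolated.

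The size is unknown. The documents give no error rates, position shares or combination rule, so nothing here shows that the algorithm would in fact over-call sitting. The gap is in the analysis text, not in data collection. It is worth fixing before analysis; confidence is medium because the wording is open to two readings.

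**What to change.** - Cross-tabulate the ankle, the thigh and the algorithm (if built) against observation over the same observed epochs.
- For each, report the percentage of observed sitting called sitting and the percentage of observed standing called sitting, with lying shown separately.
- Extend the planned three-position kappa to the algorithm if it outputs all three positions.
- Judge hypothesis 3 on sensitivity for sitting together with specificity against standing. Do not judge it on sitting agreement alone, or on a pooled kappa or balanced accuracy alone.
- State whether the algorithm's criterion is observed sitting epochs only or sitting versus not sitting over all epochs.

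The cost is a few sentences in the statistical section and a few extra table cells. Positions and their times are already recorded against one-second accelerometer data (Study procedure), so no new data and no extra burden on participants are involved. The algorithm's result may look less favourable.

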The Actigraph GT3X accelerometer contains measurement modes which quantify physical activity intensity (registering a numerical 'count'), body position via an inclinometer (lying, sitting or standing) and step count. Studies have shown good inter-instrument reliability in this particular make and model (Santos-Lozano et al., 2012). These measurement modes could permit objective, unobtrusive monitoring of all purposeful activity undertaken during the day by those recovering from critical illness in hospital. Activity may involve a postural change (sitting to standing for example), walking independently or with assistance (mobilisation) and other generalised physical activity. It could also identify where prolonged periods of inactivity are being observed, assisting in identifying individuals who may lack confidence or motivation, despite being able to undertake movement under their own volition. If used in this way, the Actigraph GT3X could assist in the effective allocation of rehabilitation resources, identifying those who may require increased input to achieve their rehabilitation goals. To date, no research has been undertaken to determine whether the Actigraph GT3X accelerometer is a valid instrument to assess body position, step count or generalised activity within a population recovering from critical illness. Despite this, recent research has used this model to objectively quantify activity levels in patients resident in the ICU, using both the inclinometer (body position) and activity count settings (Schujmann et al., 2015). The study by (Schujmann et al., 2015) placed the accelerometer on the ankle. Although manufacturer's recommend that this device is worn around the waist (Actigraph 2009), encouraging results have been found with an ankle placement, particularly in determination of step count (Korpan et al., 2015). It is important therefore to determine the validity of this particular device and its optimum body placement site within a patient population recovering from critical illness.

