Advice has been sought from the HEYHT Tissue Viability Team during construction of this methodological protocol. The inclusion and exclusion criteria have been constructed in such a way to consider those populations where placement of the accelerometers may pose additional and unnecessary risk. An assessment form has been constructed with advice from the same team to use when undertaking the half hourly assessment of skin integrity and circulation of participants during the data collection period. The Tissue viability team borrowed the accelerometers to assess whether they posed any significant risk to tissue viability and to assist in construction of the eligibility criteria for participation.

Data collection process

A data collection sheet will be populated during the data collection period. Rest periods and the positions participants adopt (e.g. lying, sitting or standing) will be recorded also.

Accelerometer data will be captured using the three different measurement modes available on the GT3X devices. Activity intensity detection is a default setting on the devices. These modes can be initialised onto the accelerometers simultaneously for eventual download onto the computer. A password protected laptop computer will be used for the initialisation of the accelerometers and subsequent data download. This laptop computer has direct remote access to the CI's personal folders on the York St John University (YSJU) virtual desktop facility, which is secure and password protected. Data files can be transferred electronically to the YSJU student virtual desktop to permit statistical analysis within SPSS.

The accelerometer settings (measurement modes) will be:

- Physical activity count (a default setting), giving a numerical score related to intensity of activity, the greater the count, the greater the acceleration of movement, hence the greater intensity
- Step count
- Inclinometer for identification of body position (lying, sitting or standing)

There are only four readings the inclinometer setting on this particular device can supply, which are detailed below:

0 = Device is off (not being worn by patient)

1 = standing

2 = lying horizontally

3 = sitting upright

Sample size calculation

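### The two-site sitting algorithm is compared with single sites scored on raw codes, so a gain from recoding cannot be told apart from a gain from the second sensor

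*Combined protocol and SAP*

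**What the plan says.** Under Statistical analysis, Categorical data, the single sites are scored on the codes as the device supplies them: "Percentage agreement of inclinometer raw data from the thigh and ankle accelerometers with direct observation for detection of each separate body position will be calculated". The code meanings are fixed in the accelerometer settings under Data collection process ("There are only four readings the inclinometer setting on this particular device can supply"): 0 off, 1 standing, 2 lying, 3 sitting.

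The two-site rule is treated differently. The investigator will examine the raw codes from both sites to see whether "an algorithm can be constructed using readings from both the ankle and thigh placement to improve determination of the sitting" position. No mapping is set in advance. On scoring, "This algorithm will be compared against direct observational raw data identifying the sitting position only". The comparison follows: "This result will be compared against the percentage agreement of the individual placement sites in determination of the sitting position". Its purpose is stated: "This will assist in determination of whether the algorithm is more superior to a single placement site in determination of the sitting position".

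Objective 3 asks whether the combined outputs can correctly determine sitting, and then names sitting versus standing as the contrast to improve. Hypothesis 3 names the same contrast.

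**The concern.** The pair and the single sites differ in two respects: the number of sensors, and the freedom to give a code a new meaning. No analysis is planned in which one site has that freedom for sitting. If the pair scores higher, the plan cannot say which difference produced the gain.

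There is reason to expect recoding to matter. The protocol notes that "manufacturer's recommend that this device is worn around the waist", so the factory labels are being read at two other sites. In a chair the thigh is roughly horizontal and the lower leg roughly vertical, so either sensor may report a label other than sitting. The feasibility result is in keeping with this: "The sitting position however was only correctly identified intermittently for the ankle placement".

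At stake is the answer to Objective 3, namely what a second device contributes beyond a better reading of one.

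**Working it through.** **The plan's own figures.** The plan gives no expected agreement for this contrast. Its cited sample size of 12 concerns a correlation and has no bearing here. The relevant figure is from the feasibility study: reading ankle code 0 as side lying moved kappa from 0.43 to 0.48, a gain of 0.05 with no second sensor. That recode concerned side lying, so it shows that recoding one site can help. It does not show by how much for sitting.

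**Illustration.** Every input below is an assumption, because the documents give no distribution of thigh codes in sitting.

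- Thigh: code 2 when sitting or lying, code 1 when standing.
- Ankle: code 1 when sitting or standing, code 2 when lying.
- Each sensor reports the other orientation with probability e, from 0.02 to 0.10.
- A share f of sitting seconds, 0 or 0.3, carries the correct code 3, independently at each site.
- Two-site rule: thigh 2 or 3 with ankle 1 or 3 is sitting; thigh 1 is standing; otherwise lying.
- Recoded thigh alone: 2 or 3 is sitting, 1 is standing.

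Share of observed sitting called sitting:

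- raw single site = f
- recoded thigh = f + (1 − f)(1 − e)
- two-site = [f + (1 − f)(1 − e)]²

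| e | f | Raw site | Two-site | Recoded thigh | Two-site minus raw | Two-site minus recoded thigh |
|---|---|---|---|---|---|---|
| 0.02 | 0 | 0% | 96.0% | 98.0% | 96.0 | −2.0 |
| 0.02 | 0.3 | 30% | 97.2% | 98.6% | 67.2 | −1.4 |
| 0.05 | 0 | 0% | 90.2% | 95.0% | 90.2 | −4.8 |
| 0.05 | 0.3 | 30% | 93.1% | 96.5% | 63.1 | −3.4 |
| 0.10 | 0 | 0% | 81.0% | 90.0% | 81.0 | −9.0 |
| 0.10 | 0.3 | 30% | 86.5% | 93.0% | 56.5 | −6.5 |

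On the planned measure the pair leads the raw sites by 56 to 96 points, and none of this is a gain over the recoded thigh.

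**Sitting versus standing.** Standing called sitting is e for the recoded thigh and e(1 − e) for the pair. Sitting agreement minus that error (Youden index) is 0.80 to 0.97 for the recoded thigh and 0.72 to 0.95 for the pair.

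**Lying.** Lying called sitting is 1 − e for the recoded thigh, or 90-98%. For the pair it is e(1 − e), or 2-9%. Agreement calculated on observed sitting alone shows neither figure.

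**All three postures.** Assume equal time in each.

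- With e = 0 and f = 0, the best thigh-only map gets (100 + 100 + 0)/3 = 67% of seconds right, and the pair 100%.
- With e = 0.05 and f = 0, thigh alone gets (95 + 95 + 0)/3 = 63.3%. The pair gets (90.25 + 95 + 90.25)/3 = 91.8%, a gain of 28.5 points. On sitting agreement alone, the same inputs put the pair 4.8 points behind.

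**What counts as best depends on the criterion.** With e = 0.05 and f = 0.3, reading thigh code 2 as sitting gets (96.5 + 95 + 0)/3 = 63.8% right over three postures. Keeping it as lying gets (30 + 95 + 95)/3 = 73.3%. The criterion must therefore be fixed beforehand and be the same for every rule.

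**The case against.** Raw codes are a legitimate baseline. Objective 1 concerns the validity of the device's own output, and whether a rule improves on the supplied labels is a practical question. This stands, and is why the raw comparison should be kept.

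The second sensor may also contribute something real. Under the geometry above, thigh code 2 means sitting or lying, and no thigh-only map can separate them; the pair can. Three of the seven items in the semi-structured movement protocol are lying positions, and the planned comparison concerns determining sitting, which includes not calling lying sitting. This stands too. A fix confined to sitting versus standing would hide the pair's contribution.

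The plan is cautious in tone: the algorithm is conditional on being constructible, the comparison only assists a judgement, and no test or threshold is attached. Each site is also first analysed separately, so a site that consistently codes sitting as something else should be visible. That softens the consequence, but seeing a consistent miscoding is not the same as scoring a recoded single site against the pair.

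A reader might infer more: that the algorithm's whole advantage would be an artefact of leg geometry, that one recoded thigh device would do, or that the study is set to conclude that patients must wear two. The documents support none of these. They report no thigh codes in sitting. Ankle sitting was sometimes correct in the feasibility study, so a raw score of exactly 0% is a limiting case only. Sitting and lying would be confused by a thigh-only rule. No conclusion about how many devices patients must wear is planned.

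**Conclusion.** The point holds as one of attribution. The planned contrast confounds recoding with the second sensor, so by itself it cannot support a statement that two sites are superior to one. This follows from the text and needs no assumption about geometry.

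The size is unknown. The 56 to 96 point lead and the 1.4 to 9.0 point shortfall against a recoded thigh are illustrations resting on the assumed orientations, error rates and share of correct codes. If a seated thigh often reads 3, the asymmetry shrinks. The sign of the second sensor's gain depends on whether lying is counted, so the conclusion is not that the second sensor adds nothing. The collected data remain usable; only the comparison needs completing before analysis.

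**What to change.** Under Statistical analysis, Categorical data:

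1. Keep the comparison with raw single-site codes.
2. Add thigh-alone and ankle-alone comparators, each with its best mapping of codes to lying, sitting and standing. State beforehand the criterion for best, and derive and test these mappings by the same procedure as the two-site rule.
3. For every rule, report correct sitting calls together with false sitting calls during observed standing and, separately, during observed lying.
4. Base any statement that two sites are superior to one on the gain over the better recoded single site across all three postures. Report the sitting-versus-standing contrast of Objective 3 alongside it.

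The cost is a change of wording and a few more cross-tabulations of data already being collected. The algorithm's apparent advantage may shrink.
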